7.3 LOST TO FOLLOW-UP

The investigational treatment will be given for 28 days. Participants will be followed for 180 days. The patients are regularly followed in clinic and will be chosen for their compliance. The proposed study is also designed to be short, only 4 weeks. All study participants will receive cards with 24-hour/7-day contact number for study team members. This approach has been sufficient to achieve a 90% retention on average in prior studies of IL-1 blockade in HF at VCU.

We will also implement a patient reimbursement of \$100 for each of 3 compled study visits (Randomization Visit, 28-day Visit, and 60-day Visit) up to a total of \$300 for completion of these study visits.

We believe this may overcome some financial barriers that our patients at VCU Health and Michigan Medicine (formerly University of Michigan Health System) may experience related to the time and cost of travel. We will collect data on enrollment and retention barriers to help enhance the success of a future phase 3 trial. The power analysis has also taken into account a potential loss of data at follow up to 20%. Missing data will not be inputted.

A participant will be considered lost to follow-up if he or she fails to return for 3 scheduled visits and is unable to be contacted by the study site staff.

The following actions must be taken if a participant fails to return to the clinic for a required study visit:

- The site will attempt to contact the participant and reschedule the missed visit within 2 weeks and counsel the participant on the importance of maintaining the assigned visit schedule and ascertain if the participant wishes to and/or should continue in the study.
- Before a participant is deemed lost to follow-up, the investigator or designee will make every effort to regain contact with the participant (where possible, 3 telephone calls and, if necessary, a certified letter to the participant's last known mailing address or local equivalent methods). These contact attempts should be documented in the participant's medical record or study file.
- Should the participant continue to be unreachable, he or she will be considered to have withdrawn from the study with a primary reason of lost to follow-up.

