6 STUDY INTERVENTION

6.1 STUDY INTERVENTION(S) ADMINISTRATION

6.1.1 STUDY INTERVENTION DESCRIPTION

We will select 28 patients and randomly assign them to treatment with anakinra 100 mg subcutaneously daily on top of standard of care or standard of care only for 4 weeks (1:1 ratio).

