9.2 SAMPLE SIZE DETERMINATION

Using an informatics-based tool by TriNetX we ran a retrospective analysis of patients seen in the Cardiac Sarcoidosis Clinic at VCU in the past year: we identified 30 subjects with sarcoidosis who had CRP 3-20 mg/L (we excluded patients with CRP>20 mg/L as they may have had concomitant bacterial infection, and therefore could be excluded upon screening). The mean age was 55 years (range 37-82), 55% were men, and 77% were African American. The CRP was 7.64 ±3.74 mg/L (mean±standard deviation). We predict a reduction of CRP by >60% in the anakinra group and no change in standard of care only group. The Table below shows estimated power for CRP reduction between 50% and 75% in the active treatment group (on top of standard of care changes, which are expected to be close to 0), and we evaluated 3 different standard deviation (SD) values starting with 3.74 mg/l which was obtained from our VCU cohort and exploring 0.9x and 1.1x SD.

Power analysis	CRP reduction (estimated mean 7.64 mg/l)					
N=28	50%	55%	60%	65%	70%	75%
SD 3.37 mg/l	85%	91%	95%	97%	99%	>99%
SD 3.74 mg/l	77%	84%	90%	94%	97%	98%
SD 4.11 mg/l	69%	77%	84%	89%	93%	96%

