9.4 STATISTICAL ANALYSES

9.4.1 GENERAL APPROACH

We will compare the change using an ANOVA for repeated measures in which we assess for the significance of the interaction of treatment allocation and time interval (time_x_group interaction) using SPSS 25.0 (Chicago, IL). Additional exploratory endpoints will include absolute CRP values at 28 days, and the percentage of patients with CRP <2 mg/L at each time point. The interval change in CRP levels from baseline to 28 days will be expressed as median and interquartile range. All reporting will be in conjunction with the CONSORT statement.¹⁹

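### Section 7.3 says the power analysis allows for up to 20% data loss, but the Section 9.2 table assumes all 28 randomised patients are evaluable; at that loss, planning-case power is about 82-84%, not 90%.

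*Combined protocol and SAP*

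**What the plan says.** Section 7.3 (Lost to Follow-Up) makes three relevant statements. On attrition and power: "The power analysis has also taken into account a potential loss of data at follow up to 20"%. On experience: "This approach has been sufficient to achieve a 90% retention on average in prior studies of IL-1 blockade in HF at VCU". On handling: "Missing data will not be inputted".

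Section 9.2 (Sample Size Determination) holds the only power analysis. It takes a mean CRP of 7.64 mg/L and an SD of 3.74 mg/L from 30 clinic patients, and states the planning effect: "We predict a reduction of CRP by >60% in the anakinra group and no change in standard of care only group". A table headed N=28 then gives power for reductions of 50% to 75% at SDs of 3.37, 3.74 and 4.11 mg/L. The planning cell (60%, SD 3.74) reads 90%. The section mentions no attrition, evaluable number, alpha level or target power.

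Section 6.1.1 fixes the number randomised: "We will select 28 patients and randomly assign them to treatment with anakinra" or to control, 1:1. Section 9.4.1 names the test: "We will compare the change using an ANOVA for repeated measures in which we assess for the significance of the interaction" of treatment and time.

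**The concern.** If 28 patients are randomised and the table is computed for 28, nothing has been set aside for loss, and the sentence in Section 7.3 describes an adjustment that was not made. The loss matters for the test itself. The primary efficacy endpoint is the change in CRP from baseline to day 28, and without imputation a patient lacking the day-28 value cannot enter the time by group comparison.

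At stake is how Section 9.2 is read. Someone who has read Section 7.3 would take the tabulated power as still holding after one patient in five is lost. If the table assumes complete data, the risk of missing a true effect at that loss is larger than the plan conveys.

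**Working it through.** **Inputs.** Mean 7.64 mg/L; SDs 3.37, 3.74 and 4.11 mg/L; reductions of 50% to 75% against no change in control (Section 9.2). 28 randomised 1:1, so 14 per arm (Section 6.1.1). Loss up to 20%, and past retention of 90% (Section 7.3). Alpha is not stated; two-sided 5% is tried first.

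**Formula.** Two-sample normal approximation, with r the proportional reduction:

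Power = Φ( r × 7.64 / [SD × √(1/n₁ + 1/n₂)] − 1.96 )

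**Step 1: reproduce the planning cell.** Difference = 0.60 × 7.64 = 4.584 mg/L. Standard error = 3.74 × √(1/14 + 1/14) = 1.414. Ratio = 3.243. Φ(3.243 − 1.96) = Φ(1.283) = 90.0%. The plan states 90%.

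**Step 2: reproduce the whole table at 14/14, no loss.**

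| SD | 50% | 55% | 60% | 65% | 70% | 75% |
|---|---|---|---|---|---|---|
| 3.37 | 85.1 | 91.0 | 94.9 | 97.4 | 98.7 | 99.4 |
| 3.74 | 77.1 | 84.4 | 90.0 | 94.0 | 96.6 | 98.2 |
| 4.11 | 69.1 | 77.2 | 83.9 | 89.2 | 93.1 | 95.8 |

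After rounding, all 17 numeric cells agree with Section 9.2, and 99.4% agrees with the remaining cell, given as >99%.

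**Step 3: test whether the table could already include the loss.** 20% of 28 is 5.6, leaving 22.4 patients, so 22 (11/11) or 23 (12/11). Numeric cells matched out of 17:

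| Reading | 11/11 | 12/11 |
|---|---|---|
| Normal, two-sided 5% | 0 | 0 |
| t-test, two-sided 5% | 0 | 0 |
| Normal, one-sided 5% | 3 | 8 |

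No loss-adjusted reading reproduces the table. With 22 patients the two-sided formula would give these figures only if the middle-row SD were 3.74 × √(1/14 + 1/14) / √(1/11 + 1/11), about 3.31 mg/L. The row is labelled 3.74.

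**Step 4: planning-case power after loss (60%, SD 3.74).** The third column is the table's formula. The last is the noncentral t, because with two time points the time by group test is a two-sample t-test on the changes.

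| Evaluable | Arms | Normal | t-test |
|---|---|---|---|
| 28 (no loss) | 14/14 | 90.0% | 87.7% |
| 25 (about 10% loss) | 13/12 | 86.5% | 83.4% |
| 23 | 12/11 | 83.6% | 79.9% |
| 22 | 11/11 | 82.0% | 78.1% |

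For 11/11 the standard error is 3.74 × √(2/11) = 1.595, the ratio 4.584 / 1.595 = 2.874, and Φ(0.914) = 82.0%.

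Loss of about 20% costs 90.0 − 83.6 = 6.4 to 90.0 − 82.0 = 8.0 points by the table's formula, or 87.7 − 79.9 = 7.8 to 87.7 − 78.1 = 9.6 points by the t-test. Moving from normal to t with no loss is a separate 90.0 − 87.7 = 2.3 points and is not part of this finding.

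**Step 5: less favourable cells at 11/11, table's formula.** A 50% reduction at SD 3.74 falls from 77% to 66.8%. A 60% reduction at SD 4.11 falls from 84% to 74.4%.

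**Step 6: sensitivity to the SD.** The 3.74 is a cross-sectional SD used as the SD of change. With equal variances, SD of change = 3.74 × √(2(1 − ρ)), which equals 3.74 only at ρ = 0.5. The documents give no ρ. Over an assumed range:

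| ρ | SD of change | t-test power, 14/14 | t-test power, 11/11 |
|---|---|---|---|
| 0.3 | 4.43 | 75.1% | 63.7% |
| 0.5 | 3.74 | 87.7% | 78.1% |
| 0.7 | 2.90 | 98.1% | 94.2% |

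The absolute level is uncertain, but the loss lowers power throughout.

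**The case against.** The best defence is that taking loss into account need not mean the table is net of loss. It may mean that 28 was judged sufficient even with 20% missing. By the table's formula the planning case stays above 80%, the prediction is a reduction of more than 60%, and no target power is stated that could be missed. This reading is possible, but Section 9.2 contains no attrition case and no threshold, so nothing in the plan documents such a judgement.

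Second, 22 evaluable patients means six lost, or 21.4%, just over the stated limit; five lost is 17.9% and leaves 23. That is correct, which is why both are shown. The 23-patient figure, 83.6%, leads to the same conclusion.

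Third, alpha and sidedness are unstated, and a one-sided reading at 12/11 comes close: 8 of 17 cells, with 90.2% in the planning cell. The two-sided no-loss reading matches all 17 and agrees with the N=28 heading, so it is much the better explanation, though still an inference.

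Fourth, the unknown SD of change moves power more than the loss does, and at the cited 90% retention the shortfall is only 90.0 − 86.5 = 3.5 points. Both points stand. They limit the practical weight of the finding, but they do not make the sentence in Section 7.3 true.

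**Conclusion.** The concern holds. The allowance claimed in Section 7.3 is absent from the only power table in the plan. At the stated loss limit, the planning-case chance of missing a true 60% reduction in CRP is 16-18% by the plan's own formula, against the 10% implied by the table.

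This rests on three assumptions: two-sided 5%, inferred from the exact match; an SD of change of 3.74 mg/L; and the loss falling on the day-28 CRP, since a patient lost after day 28 still contributes.

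The primary objective is feasibility and no CRP significance rule decides whether a further trial follows. This is therefore an error in a stated design property that should be corrected, and it does not invalidate the design.

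**What to change.** Keep 28 patients and reconcile Sections 7.3 and 9.2 in one of two ways.

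1. Restate the Section 9.2 table for 22 evaluable patients. Name the test and alpha, and say that 3.74 mg/L is a cross-sectional SD taken as the SD of change. Across reductions of 50% to 75%, the SD 3.74 row would read about 67/75/82/88/92/95% by the present formula, or 62.5/70.8/78.1/84.2/89.0/92.7% by the t-test. If 23 is preferred as the number within the 20% limit, the present formula gives about 69/77/84/89/93/96%.
2. Label the present table as assuming all 28 evaluable with no loss, and delete the 20% sentence from Section 7.3.

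The first is more informative, because it keeps an attrition assumption and shows its effect. Preserving the tabulated power after 20% loss would instead need 28 / 0.8 = 35 randomised (36 for equal arms), which a feasibility pilot does not require.

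The cost is a sentence in Section 7.3 and one table or table label in Section 9.2. No patients are added and neither endpoint nor analysis changes. Under the first option the stated power is less favourable.

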8 STUDY ASSESSMENTS AND PROCEDURES

8.1 EFFICACY ASSESSMENTS

8.1.1 Biomarkers

Blood samples will be taken from a peripheral vein at time of screening, randomization visit and the 28day visit, and used for analysis of inflammatory markers - high-sensitivity C reactive protein (CRP) and Interleukin-6 (IL-6).

Samples will be processed by the Department of Pathology at VCU or UMich, as standard of care tests are processed.

We will compare interval changes in CRP and IL-6 between the 2 groups using an analysis of variance (ANOVA) for repeated measures and assessing for time_x_group interaction.

Additional exploratory analyses will be conducted on cytokines from sera of patients with bioassays available through LabCorp.

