6.3 MEASURES TO MINIMIZE BIAS: RANDOMIZATION AND BLINDED ASSESSMENT

Randomization will be handled by a member of the research team not involved in the consenting process using a dedicated randomization algorithm, stratified by center (VCU / UMich) and by race/ethnicity (Caucasian / Others).

Assessment of ECG Holter and of imaging, for substudy, will be performed by operators who are blinded to treatment allocation.

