9 STATISTICAL CONSIDERATIONS

9.1 STATISTICAL HYPOTHESES

• Primary Efficacy Endpoint(s):

Interval change in CRP levels from baseline to 28 days

We hypothesize that anakinra will reduce systemic inflammation as shown by CRP levels. CRP will be measured with a widely available high-sensitivity assay able to detect values in the normal range (<2 mg/l). Hs-CRP will be measured at randomization visit and again at 28±3 days. We will use ANOVA for repeated measures and assess time_x_group interaction to determine differences between changes in the anakinra on top of standard of care group versus standard of care only group.

• Secondary Efficacy Endpoint(s):

Interval change in IL-6 levels from baseline to 28 days

We hypothesize that anakinra will reduce systemic inflammation as shown by IL-6 levels. IL-6 will be measured with a widely available ELISA assay . IL-6 will be measured at randomization visit and again at 28±3 days. We will use ANOVA for repeated measures and assess time_x_group interaction to determine differences between changes in anakinra group versus control group.

Interval change in QoL scores at SAT

We hypothesize that anakinra will improve QoL scores on SAT questionnaires. QoL SAT will be measured at enrollment and again at 28±3 days. We will use ANOVA for repeated measures and assess time_x_group interaction to determine differences between changes in anakinra group versus control group

• Additional Efficacy Endpoints(s) for Imaging Substudy available at VCU

[Interval change in T2 mapping at CMR]

[We hypothesize that anakinra will reduce myocardial edema as measured by T2 mapping at CMR. T2 mapping will be completed within 30 days of randomization and again at 28 ± 14 days. We will use ANOVA for repeated measures and assess time_x_group interaction to determine differences between changes in anakinra versus control.]

[Interval change in cardiac FDG-PET inflammation signal]

[We hypothesize that anakinra will reduce myocardial inflammation as measured by cardiac PET signaling. PET signaling will be completed within 60 days of randomization and again at 28 ± 14 days. We will use ANOVA for repeated measures and assess time_x_group interaction to determine differences between changes in anakinra versus control.]

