9.4.3 ANALYSIS OF THE SECONDARY ENDPOINT(S)

We will measure changes in IL-6, an additional inflammatory biomarker as a secondary endpoint. Changes in QoL scores will also be considered a secondary endpoint.

Additional secondary endpoints to be completed as part of the imaging substudy at VCU includes assessment of myocardial edema with T2 mapping at CMR, and myocardial inflammation with cardiac FDG-PET.

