9.4.7 SUB-GROUP ANALYSES

Randomization will be stratified by site (VCU and UMich) and by race/ethnicity. Two pre-specified subgroup analyses includes site and race/ethnicity.

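### IL-6 is measured in two hospital laboratories with no requirement that the assays be comparable, and raw changes are then pooled; a log-ratio analysis with centre in the model would remove any proportional difference between them.

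*Combined protocol and SAP*

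**What the plan says.** Section 8.1.1 covers CRP and IL-6 together and leaves measurement to each hospital: "Samples will be processed by the Department of Pathology at VCU or UMich, as standard of care tests are processed". For the IL-6 method, section 9.1 says only that "IL-6 will be measured with a widely available ELISA assay". It gives no manufacturer, calibrator, unit, lower limit or cross-laboratory check. For CRP the same section at least asks for a high-sensitivity assay that reads into the normal range. Section 8.1.1 uses a single outside laboratory only for further markers: "Additional exploratory analyses will be conducted on cytokines from sera of patients with bioassays available through LabCorp".

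On analysis, section 8.1.1 states: "We will compare interval changes in CRP and IL-6 between the 2 groups using an analysis of variance (ANOVA) for repeated measures". Section 9.4.1 rests the test on "the interaction of treatment allocation and time interval (time_x_group interaction"). No transformation and no site or stratum term is given. Centre enters the plan twice elsewhere. Section 6.3 says randomisation is "stratified by center (VCU / UMich) and by race/ethnicity (Caucasian / Others"), and section 9.4.7 says: "Two pre-specified subgroup analyses includes site and race/ethnicity".

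On the role of IL-6, section 9.4.3 says: "We will measure changes in IL-6, an additional inflammatory biomarker as a secondary endpoint". Section 9.1 agrees. The synopsis lists IL-6 beside CRP as an efficacy endpoint.

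**The concern.** Two routine laboratories can report the same sample on different scales. Where they do, a one-unit fall at one site is not a one-unit fall at the other, and an average of raw changes mixes the two. The site with the larger numbers then counts for more in the estimate and contributes most of the noise.

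Section 4.2 says the pilot is meant to estimate an effect size for later trials. An IL-6 difference averaged over two scales would be hard to carry forward.

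Reporting limits are a related gap. Eligibility requires CRP of at least 2 mg/L but sets no minimum for IL-6. A patient whose baseline is already at a laboratory's reporting limit cannot show a fall, and the plan states neither the limits nor how such values are handled.

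**Working it through.** **Inputs from the documents.** 28 patients, 1:1, so 14 per arm (section 6.1.1). Each site expects 8-10 patients a year, UMich at least that many (section 5.5), so equal sites are taken: 7 per arm per site. CRP mean 7.64 and SD 3.74 mg/L, 60% reduction against no change (section 9.2). The documents give no mean, SD, effect or power for IL-6.

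**Assumptions.** Two-sided alpha of 0.05 (none is stated). A site scale ratio *k*, which the documents do not give, is shown as a range. Each patient's two samples go to the same laboratory. All 28 patients are analysed.

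**The plan's own figure.** Standardised effect = 0.60 × 7.64 / 3.74 = 4.584 / 3.74 = 1.23. By the normal approximation, 1.2257 × √(14/2) − 1.960 = 3.243 − 1.960 = 1.283, and Φ(1.283) = 0.90. This matches the 90% in the section 9.2 table. The noncentral *t* distribution gives 0.877. This is a CRP figure, used for IL-6 only as a stand-in.

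**Weighting.** Let the true change be δ with SD σ at one site, and let the other laboratory read *k* times higher. With equal sites:

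- pooled difference = (δ + *k*δ)/2, so the higher-reading site's share is *k*/(1 + *k*);
- average error variance = (σ² + *k*²σ²)/2, so its share is *k*²/(1 + *k*²).

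**Power.** With two time points, the time-by-group test is a *t*-test on change. Power was simulated with 40,000 trials per setting, once at the CRP-derived effect and once at an assumed 1.1 SD, where power is about 80% on a common scale.

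| *k* (assumed) | Share of effect | Share of error variance | Power, CRP-derived effect | Power, 1.1 SD | Power, 1.1 SD, raw change plus site term |
|---|---|---|---|---|---|
| 1 | 50% | 50% | about 87% | 80% | 80% |
| 1.5 | 60% | 69% | 86% | 78% | 78.5% |
| 2 | 67% | 80% | 83% | 74.5% | 75% |
| 3 | 75% | 90% | 77% | 68% | 70.5% |

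At *k* = 1.2 the shares are 55% and 59%, and power at 1.1 SD is 79.5%, which is hardly a loss. The last column shows that a site term on raw values recovers almost nothing: it removes a difference in average change between sites, not a difference in scale.

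**Type I error.** With no treatment effect, rejection rates were about 0.05 with normal data and 0.035-0.042 with skewed data on the raw scale.

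**Log ratio.** log(*k*·Y₂₈ / *k*·Y₀) = log(Y₂₈ / Y₀), so a proportional site factor cancels. IL-6 was simulated as log-normal (assumed: median baseline 4, log-scale SD 0.6 at baseline and 0.5 for the change, 50% fall against none). Raw change had power 0.78, 0.73 and 0.68 at *k* = 1, 2 and 3. The log ratio had 0.94 at every *k*, and a centre term leaves that unchanged to two decimals. Most of this gain comes from handling skewness, since 0.78 against 0.94 arises at *k* = 1.

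**The case against.** The strongest reply is that the premise is not shown. No section says that the laboratories use different assays, and the singular wording in section 9.1 fits one kit at both sites. Section 10.1.10 refers to a manual of procedures that is not among the documents and could specify the assay. This stands: the gap is a missing requirement, not a demonstrated mismatch.

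The size also rests on assumption. The ratios have no source in the documents, the effect is borrowed from CRP, and IL-6 has no planned power to lose. That stands too. At a ratio of 1.5 the loss is a point or two.

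A reader might infer three stronger things that the documents do not support:

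- **A result biased towards anakinra, or too many false positives.** Arms are balanced within centre by stratification, and the simulated error rate does not exceed 0.05 beyond simulation noise.
- **One site dominating the result.** That word fits only from about a two-fold difference, and no such difference is documented.
- **The missing site term being the fault.** Adding it to raw values barely helps.

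The site subgroup analysis in section 9.4.7, applied to IL-6, would show each site's effect in its own laboratory's units and could expose a mismatch. It would not correct the pooled test.

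**Conclusion.** The point holds in a limited, conditional form. The plan does not require comparable IL-6 assays, and it pools raw changes in a way that is sensitive to any difference in scale. If the scales differ, the cost is unequal weighting of sites (60% to 75% on the higher-reading site for ratios of 1.5 to 3), an estimate without a clear unit, and a modest loss of power (about 87% down to 86%, 83% or 77%). These figures assume equal enrolment, the CRP-derived effect and no loss to follow-up. If the assays agree, this cost is nil. The validity of the test is not in question. Because IL-6 is secondary in a 28-patient feasibility pilot, this is a minor improvement, worth making because it is nearly free.

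**What to change.** In sections 8.1.1 and 9.1, and in 9.4.1 so far as it governs IL-6, define the IL-6 analysis as the log of the day-28 to baseline ratio. Compare it between arms with centre, a stratification factor, in the model, and report the effect as a percentage change with its confidence interval. This stays close to the planned method: the time-by-group test on log values with two time points is a test of the log ratio.

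Also name the assay used at each site, state each laboratory's lower reporting limit, and say how values at the limit are handled. The log ratio cancels a proportional difference but not a floor effect, nor a constant offset between assays.

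Measuring IL-6 from both sites in one laboratory would settle comparability directly and is optional, if feasible. The documents do not show that the outside laboratory offers IL-6 or what it would cost, nor do they give a specimen plan for that work.

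Cost: analysis-plan wording, a result expressed as a ratio rather than in concentration units, and one degree of freedom for centre, or two if race/ethnicity is added as well.
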